8. SAFETY ANALYSES

All safety analyses will be done for the safety population and reported in tabular forms. These analyses include serious adverse events and laboratory measurements.

8.1. Serious Adverse Events

Serious adverse events (SAEs) are defined by the ICH for Clinical Safety Data Management (ICH-E2A), the Food and Drug administration (21CFR312.32) and CSP Global SOP 3.6, as described in the section 4.4.3. Incidence of SAEs will be summarized for each intervention group by body system and MedDRA term. The number and percentage of participants with each body system and MedDRA term will be presented for each intervention group (Table 29). A list of SAEs where deaths of randomized participants are indicated will be created (Table 30).

8.2. Laboratory Measurements

Laboratory measurements including Hemoglobin (gm/dl), Troponin (ng/ml), and Creatinine (mg/dl) are measured during the participants hospital stay. For each measurement, the sample size, median, lower quartile, upper quartile, minimum, and maximum values for the daily lowest value of each lab variable on randomization day, post-randomization Days 1, 2, 3, 4, 7 and discharge day in each intervention group will be presented (Table 31).

REFERENCES

7. Whitaker BIS, K.;Schulman,J.;Green,J. The 2009 national blood collection and utilization survey report. 2011. Accessed October 14, 2011, 2011.

Appendix 1. Study Flow

Appendix 2. Data Collection Schedule

599	Pre-Randomization			Post-Randomization Days										Follow-Up		
	Pre-Screening		Index Operation	Post-Op Day 1-15		Post-Randomization Days							Post-Randomization Day +			
	Pre-Op	Consent		Randomization Day 0	R-Day 1	R-Day 2	R-Day 3	R-Day 4	R-Day 5	R-Day 6	R-Day 7	Additional	Discharge	30 Days (±7 days)	90 Days (±14 days)	1 Year
Fm 86 Consent Confirmation		R														
Fm 1 Consent Randomization	p1	T(p2,3)	T	T	R(p4,5)											
Fm 2 Participant History/Clinical Data														R**		
Fm 3 Hemoglobin					R	R	R	R	R	A	A	R	A****	RA		
Fm 4 Transfusion Record					A	A	A	A	A	A	A	A	A	A		
Fm 6 Laboratory Markers***					R	R	R	R	R	A	A	R		R***		
Fm 7 Patient Status														R	R	
Fm 8 MI Confirmation														A	A	
Fm 9 Infect/Cardiac Complications														R	R	
Fm 10 Participant Status at 1 Year*																R*
Fm 11 SAE														From Randomization +90 days or Termination		
Fm 12 SAE Follow Up														Follow-up SAE every 30 Days until resolution, stabilization, PR +90 days or Termination		
Fm 13 Protocol Deviation		A	A	A	A	A	A	A	A	A	A	A	A	Rp5		
Fm 14 Participant Termination*****					A	A	A	A	A	A	A	A	A	A	A	A
Fm 19 COVID-19 Exclusion Criteria*	R	R												R		
Post-Operation																
Fm 5 Medical Orders	Day -1	Day 0	Day 1	Day 2										Day 3+		Discharge
	E	E	E	E											R	

Note: *Chairman's office use only; Related time periods; A = If Actionable; E = Req. Form Entry if Randomized; R=Req. entry/complete form; Rp5=Req. per SAE; T=Data req. even if not randomized; PR=Post-randomization; D/C=discharge; RA=Hb collected PR Day 0-4,7 and/or D/C and according to ***standard clinical practice; **Req. if eligible but not randomized; ***Labs are collected PR Day 0-4, 7 and/or D/C (if PR day before Day 7); ECGs are collected PR Day 0, 1 & 4 or D/C if D/C is before Day 4; ***** Only one Form 14 req per participant. p1= Pre-Op use Form 1 Page 1. t(p2,3)=Once consented consider form 1: pages 2 & 3 part of pre-screening. R(p4,5)=If Randomized use Form 1: page 4 & 5. *See Form 19 for details.

[figure not shown]
PROTOCOL Version 6

Image Version 11/30/2021

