Participants will be given an appointment for a clinic visit within one week after the 30 post-randomization day. Questions regarding symptoms related to MI, other cardiac events, stroke, pneumonia, and wound infection will be asked. If a participant has a readmission prior to the 30 day post-randomization time point, then the electronic medical record, will be reviewed to determine whether the reason for admission includes any of the complications that consist of the primary or other study endpoints, such as coronary revascularization or acute renal failure. If the participant has been admitted to a non-VA hospital, then complete records from this admission will be obtained from that hospital to document the reason for admission and whether any of the study endpoints have been developed which led to the readmission. The hospital records obtained will include History and Physical, all consultations, procedures, laboratory values, fluid cultures, copies of EKG and Echocardiography reports, as well as reports from all imaging studies performed, catheterization laboratory reports and operating room reports. To assure access to these records, release of information forms will have to be signed by the participant as part of the initial informed consent process. If the participant does not present for the follow up within two weeks from the anticipated appointment time, an electronic medical record review and phone call follow-up will be performed and focused questions will be asked, to identify the occurrence of any of the endpoints. Questions about interval readmission will also be asked at the follow up visit/call.

b) Ninety Day Follow-up

Participants will be given a clinic appointment within two weeks after the 90th post-randomization day. Questions regarding symptoms related to cardiac events, stroke, infectious complications will be asked as described above for the 30-day post-randomization follow up. If participants are unable to make the clinic visit within two weeks of the assigned appointment then an electronic medical record review and phone call follow-up will be performed as described above. Readmissions since previous follow-up will also be investigated with similar series of actions as with the 30 day post-randomization follow-up. Pertinent laboratory values (creatinine, troponin), EKG results, cardiac catheterization reports and operating room reports since the previous visit will be

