3.2. Study Outcome Variables

3.2.1. Primary Outcome Variable

The primary outcome is defined as a composite endpoint of all-cause post-randomization mortality, myocardial infarction (MI), coronary revascularization, acute renal failure, or post-randomization ischemic stroke up to 90 days after randomization.

MI will be defined using the Third Universal Definition of Myocardial Infarction.²⁸

Acute renal failure will be defined as Acute Kidney Injury stage III according to RIFLE criteria: Serum creatinine rise greater than 3 times that of baseline creatinine; or if baseline serum creatinine is greater than 4 mg/dl, then rise more than 0.5 mg/dl compared to baseline; or urine output less than 0.3ml/Kg/hr for 24 hours; or anuria for 12 hours. Baseline creatinine will be considered the creatinine upon admission prior to the index operation. The above urine output criteria will be only used for patients who are in the ICU and have precise monitoring of their urinary output. For patients on the surgical floor only serum creatinine changes will be used for assessment of this endpoint.

Coronary revascularization will be defined as a coronary artery bypass graft, or percutaneous coronary intervention (either angioplasty or stenting).

Stroke will be defined as new unilateral neurological deficit that lasts for more than 24 hours and is confirmed by a brain imaging modality (either computed tomography or magnetic resonance imaging study) demonstrating new brain infarct.

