4. STUDY METHODS

4.1. General Study Design

The study is a parallel, single-blind, controlled, superiority trial in which participants will be randomized to a restrictive or a liberal transfusion group. This study will randomize 1520 Veterans at 15 VA Medical Centers. The total recruitment period will be approximately 4 years which will be followed by a 3 month active and 9 month passive follow-up period. The duration of the study will be approximately 5 years. Consent for the study will be obtained prior to the index surgical intervention at the clinic visit or, in case of inpatients, at the hospital ward pre- or postoperatively. Randomization will be performed via a central telephone randomization system once the participant has a confirmed post-operative Hb < 10gm/dl. Active follow up will be up to three months after randomization. Passive follow up will be from 3 months to one year after randomization. The study flow is shown in Appendix 1. There will be no blinding at the treating physician level; however the participants and the Endpoint Committee will be unaware of group allocation.

Follow up forms will be filled out during two postoperative clinic visits that will be after the 30th and 90th post-randomization days. Participants who cannot make the clinic visits will be assessed by phone call follow-up, during which they will be asked specific questions to ascertain whether signs or symptoms related to any of the endpoints have developed. In

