4.4.2. Follow-up Assessment

Follow-up assessments will be collected after participants discharged from hospital including 30- day and 90-day active follow-up assessments and one-year passive follow-up assessment.

Thirty Day Follow-up: Participants will be given an appointment for a clinic visit within (+/-) one week after the 30 post-randomization day. Questions regarding symptoms related to MI, other cardiac events, stroke, pneumonia, and wound infection will be asked. If a participant has a readmission prior to the 30-day post-randomization time point, then the electronic medical record, will be reviewed to determine whether the reason for admission includes any of the complications that consist of the primary or other study endpoints, such as coronary revascularization or acute renal failure. If the participant has been admitted to a non-VA hospital, then complete records from this admission will be obtained from that hospital to document the reason for admission and the development of study endpoints leading to readmission. The hospital records obtained will include History and Physical, all consultations, procedures, laboratory values, fluid cultures, copies of EKG and Echocardiography reports, as well as reports from all imaging studies performed, catheterization laboratory reports and operating room reports. To assure access to these records, release of information forms will be signed by the participant as part of the initial informed consent process. If the participant does not present for the follow up within two weeks from the anticipated appointment time, an electronic medical record review and phone call follow-up will be performed and focused questions will be asked, to identify the occurrence of any of the endpoints. Questions about interval readmission will also be asked at the follow up visit/call.

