Ninety Day Follow-up: Participants will be given a clinic appointment within two weeks (+ only) after the 90th post-randomization day. Questions regarding symptoms related to cardiac events, stroke, infectious complications will be asked as described above for the 30-day post-randomization follow up. If participants are unable to make the clinic visit within two weeks of the assigned appointment then an electronic medical record review and phone call follow-up will be performed as described above. Readmissions since previous follow-up will also be investigated with similar series of actions as with the 30-day post-randomization follow-up. Pertinent laboratory values (creatinine, troponin), EKG results, cardiac catheterization reports and operating room reports since the previous visit will be reviewed in the electronic medical record to ascertain the presence of coronary revascularization, stroke, MI, or acute renal failure.

One Year Follow-up: Follow up will be performed by trained staff from the Chair's office at twelve months after randomization to ascertain vital status. The CSPCC will generate listings of participants due for follow-up which will be sent to the Chairman's personnel responsible for conducting the telephone interviews. Follow-up data will be obtained by study staff. This removes the need for personal identifying information to be maintained at the individual sites or the CSPCC and helps to protect participant confidentiality. Study participants will be called, chart reviews will be performed, and the VHA Death Ascertainment File (DAF) data will be used to determine a participant's death and date of death. The DAF will be used to assess the one-year vital status of those participants discharged alive from the hospital for whom vital status cannot be determined. Social Security number will be used to obtain the patient identifier PatientICN, which will be necessary for linkage to the DAF. The data collection schedule as shown in Appendix 2.

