7.1. Primary Endpoint Analysis

The primary study endpoint will be a composite outcome of all-cause mortality, MI, coronary revascularization, acute renal failure, or post-randomization stroke within 90 days from randomization. A clinical events committee will adjudicate all component events for the primary endpoint. The number and percentage of participants with the composite endpoint at the 90-day visit after the randomization will be summarized and compared according to assigned transfusion strategy (analysis by intent to treat) using Pearson χ^2 test. Another analysis will compare primary endpoint between the two transfusion strategies stratified by clinical sites using the Cochran-Mantel-Haenszel test (Table 16a-e). The test for differences between transfusion strategies in the primary outcome will be conducted at an overall α -level of 0.05. Additional analysis will be conducted using logistic models to adjust for other clinical factors, such as age, RCRI, and nadir Hb. The interactions of the intervention with age, RCRI and nadir Hb will also be considered.

Odds ratio and 95% confidence interval (CI) will be presented using SAS PROC GENMOD or PROC LOGISTIC. Assumptions of the model including linearity in the logit of the composite event risk for continuous variables will be checked. We will assess goodness-of-fit using the statistic -2 log likelihood, which has a chi-square distribution under the null hypothesis that all the explanatory variables in the model are not associated with the outcome

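### SAP Appendix 2 puts the 90-day visit in window from day 76 while the text places it after day 90, so a few late non-fatal primary events may be missed

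*SAP*

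**What the plan says.** The SAP gives two windows for the same visit.

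- **SAP Appendix 2 (Data Collection Schedule):** the follow-up column is headed "90 Days (±14 days".
- **SAP 4.4.2, Ninety Day Follow-up:** "Participants will be given a clinic appointment within two weeks (+ only) after the 90th post-randomization day". This subsection ends by referring the reader to Appendix 2.
- **SAP 4.1:** follow-up forms are completed at "two postoperative clinic visits that will be after the 30th and 90th post-randomization days". Protocol VI says the same.
- **Protocol IX.C.2(b), Ninety Day Follow-up:** "Participants will be given a clinic appointment within two weeks after the 90th post-randomization day".

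For the 30-day visit, SAP 4.4.2 uses a two-sided window: "Participants will be given an appointment for a clinic visit within (+/-) one week after the 30 post-randomization day". Appendix 2 agrees with that one.

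The primary outcome in SAP 3.2.1 runs to a fixed horizon, ending with "post-randomization ischemic stroke up to 90 days after randomization". SAP 7.1 first defines the endpoint as occurring within 90 days of randomization, then says the analysis will tabulate "participants with the composite endpoint at the 90-day visit after the randomization".

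**The concern.** SAP 4.4.2 marks the 30-day window as two-sided and the 90-day window as one-sided. That looks deliberate: a visit held no earlier than day 90 can ask about the whole endpoint period. Appendix 2 removes that property. Under it, a visit on day 76 is compliant and leaves up to 14 days of the endpoint period after the last scheduled endpoint assessment.

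In Appendix 2 the 90-day visit is the last one that carries Forms 7, 8 and 9 (patient status, MI confirmation, infectious and cardiac complications). The one-year contact ascertains vital status only. No rule says what to do for a participant seen on days 76 to 89, and the phrase in SAP 7.1 that ties the count to the visit does not settle it.

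Two other quantities depend on the window. SAP Table 7 counts 30- and 90-day visits held outside the window as deviations. The Completers population in SAP 5.4 requires assessment of the five components at the 90-day follow-up. A day-80 visit is compliant or a deviation depending on which window applies, and whether it makes the participant a completer is left open.

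**Working it through.** **1. The two windows.** Appendix 2: 90 − 14 = day 76 to 90 + 14 = day 104. SAP 4.4.2: after day 90, up to day 104. The largest part of the endpoint period that can follow an in-window visit is 14/90 = 15.6% under Appendix 2 and nothing under 4.4.2.

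**2. What still reaches day 90 without the visit.**

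| Route | Where | Limit |
|---|---|---|
| Active follow-up defined by time, to 90 days | Protocol IX.D.2 | Sets the period; schedules no further contact |
| SAE reporting to day 90 | Protocol XI.D; SAP 4.4.3; Form 11 row of Appendix 2 | Site must learn of the event; Protocol XI.B ties participant monitoring to follow-up visits |
| Record review for readmissions within 90 days, including non-VA records | Protocol VI; SAP 4.1 | Readmission must be known; interval readmission is asked about at the visit or call |
| Dated deaths from one-year follow-up | SAP 4.4.2 | Deaths only |

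What remains exposed is a non-fatal MI, stroke, acute renal failure or revascularization, after an early visit and by day 90, in someone with no earlier component event, chiefly when treated outside the VA and not reported to the site.

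**3. The plan's sample size, reproduced.** Inputs from SAP 4.5: 30% vs 22.5%, two-sided 5%, power 90%. With p̄ = 0.2625:

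n per arm = [(1.960·√(2·0.2625·0.7375) + 1.282·√(0.30·0.70 + 0.225·0.775)) / 0.075]² ≈ 721.2, rounded up to 722, so 1444 in total. Then 1444/0.95 = 1520. Both match the SAP. Expected events among 1444 are 1444 × 0.2625 ≈ 379.

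**4. What an early visit could cost, under stated assumptions.** The documents give no event timing and no share of early visits. Let s be the share of events falling after day 76 and by day 90, and f the fraction of participants seen on day 76. Assume the same loss in both arms and no recovery by the routes in step 2. Then loss l = s × f, the observed rates are 0.30(1 − l) and 0.225(1 − l), and

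power = Φ{[d·√722 − 1.960·√(2p̄q̄)] / √(p₁q₁ + p₂q₂)}, where d = p₁ − p₂, p̄ is the mean of the two rates, and q = 1 − p.

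| s | f | l | Observed rates | Events missed of 379 | Power |
|---|---|---|---|---|---|
| 0 | – | 0 | 30.0% vs 22.5% | 0 | 90.0% |
| 2% | 50% | 1% | 29.7% vs 22.3% | 3.8 | 89.6% |
| 5% | 100% | 5% | 28.5% vs 21.4% | 19.0 | 88.0% |
| 15.6% (constant rate) | 100% | 15.6% | 25.3% vs 19.0% | 59.0 | 82.6% |

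Check of the second row: d = 0.297 − 0.22275 = 0.07425 and p̄ = 0.259875. The numerator is 1.995 − 1.216 = 0.779 and the denominator 0.618. The ratio 1.261 gives 89.6%.

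The last row is an extreme: everyone seen on day 76, a constant event rate, and nothing recovered. If postoperative events cluster early (an assumption) and the other routes work in part, the loss lies towards the top of the table.

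**The case against.** The case against giving this much weight is good, and most of it stands.

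- **The schedule is one item against four.** SAP 4.1, SAP 4.4.2, Protocol VI and Protocol IX.C.2 all place the visit after day 90. The schedule image is stamped Protocol Version 6, dated 11/30/2021, while the Protocol is Version 11, dated 12/18/2024. It is probably outdated. A misread plus sign in the PDF cannot be fully excluded, although the ±7 days at day 30 in the same row agrees with the text.
- **A reader might infer that sites work from this schedule.** The documents do not say so. It is an appendix to the statistical plan, and case report forms and SAE forms are completed under the Operations Manual.
- **A reader might infer that an early visit closes follow-up.** It does not. Active follow-up, SAE reporting and readmission review are all defined to day 90. Hospital admission and death are SAE criteria, so most late component events would be reportable whatever the visit date.
- **A reader might infer that non-VA events would be undetectable.** Full non-VA records are to be obtained for readmissions within 90 days, with release given at consent. Deaths are dated independently. In Protocol Table 2, for nadir Hb 6–9 gm/dl, death is 15.3% against a composite of 29.5%, so about half of composite cases (15.3/29.5 = 52%) include a death.
- **The endpoint is already defined by time.** SAP 3.2.1 and the first sentence of SAP 7.1 both do so. The visit phrase can be read as a label for the tabulation.

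These points limit the consequence but do not remove the contradiction. Appendix 2 is part of the current SAP, and 4.4.2 itself points to it. The capture routes rely partly on contact: after an early visit, no later contact is scheduled by day 90 that would bring an undisclosed outside admission to light.

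**Conclusion.** The contradiction is real and should be corrected. It is an internal inconsistency, since the text already states a consistent design. Its certain effect is that visits on days 76 to 89 are classified differently by the two windows. Its possible effect is the loss of some late non-fatal component events, mainly those treated outside the VA and not otherwise reported.

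The loss is probably small, but the documents do not allow it to be computed. The mild scenario (about 4 of 379 events, power 89.6%) is an illustration, and the 82.6% case needs conditions that nothing in the documents suggests. A reader might also assume that half of events fall in the first 10 days and the rest evenly over the next 80, giving 0.5 × 14/80 = 8.75% lost. That figure applies only to a participant seen exactly on day 76 with no recovery from other sources, and the timing split has no basis in the documents. It is not a trial-level effect.

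Nothing suggests that early visits differ between arms, so the documents do not support a claim of bias between the groups.

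**What to change.** 1. In Appendix 2, change the column heading to 90 Days (+14 days), to match SAP 4.4.2, and replace the Version 6 image with a current schedule.
2. In SAP 7.1, replace the reference to the 90-day visit with a count of participants whose first component event is dated on or before day 90 after randomization, whatever the visit date.
3. Before database lock, list every 90-day visit held before day 90. For those participants, complete the record review through day 90, with a short call where possible. The consent release already covers hospital visits within 90 days.
4. State that the corrected window governs the Table 7 deviation count, and say how an early visit is treated in the Completers definition.
5. In the same revision, reconcile the 30-day window: Protocol IX.C.2(a) places that visit within one week after day 30, while SAP 4.4.2 and Appendix 2 allow a week either side.

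The cost is a wording change and a little extra record review for early visits. The planned rates, the 1444 evaluable and 1520 randomized participants, and the 90% power are unaffected.

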Appendix 3. Power Analysis

90 Day Composite Endpoint (%)				Power (%)			
Liberal	Restrictive	Difference	Percent Difference	75	80	85	90
17.50	25.00	7.50	30.0	826	932	1066	1248
18.75	25.00	6.25	25.0	1214	1372	1570	1836
20.00	25.00	5.00	20.0	1936	2188	2502	2928
21.00	30.00	9.00	30.0	650	734	840	982
22.50	30.00	7.50	25.0	954	1080	1234	1444
24.00	30.00	6.00	20.0	1520	1718	1964	2298
24.50	35.00	10.50	30.0	526	594	678	794
26.25	35.00	8.75	25.0	770	870	994	1164
28.00	35.00	7.00	20.0	1222	1382	1580	1848

